15.5.1 Power calculations for Phase B

For primary endpoints of HIV incidence, we present the following power calculations based on *inctools R* package,¹ which implements and extends the HIV incidence methods of Kassanjee et al.¹¹² The *R* package is a more robust implementation of the prior ABIE (Assay Based Incidence Estimation) spreadsheet tool, developed by the CEPHIA (Consortium for the Evaluation and Performance of HIV Incidence Assays). When possible, we used prior data to inform key parameters, including (i)community size, (ii) HIV prevalence, (iii) expected testing coverage, (iv) expected outcome under the standard-of-care, and (v) recency assay characteristics.^{2,3} We expect these calculations to be conservative, because of the precision gained through our pre-specified choice of a one-sided hypothesis test and through covariate adjustment during the analysis.^{5, 104, 106}

With 16 communities (8 per arm) each with ~5000 adults, 10% HIV prevalence, and 90% testing coverage, we anticipate being powered at 80% to detect a 40% relative reduction in annual HIV incidence from 0.5% in the standard-of-care (control) with a two-sided hypothesis test ($\alpha=0.05$), a design effect of 1.3, mean duration of recent infection (MDRI) of 238, and false recent rate (FRR) of 0%. As shown in **Figure 6**, these calculations are fairly robust to the test coverage achieved and HIV incidence under the standard-of-care.

[figure not shown]

Figure 6: For the Phase B cluster randomized trial, the effect size (in relative reduction in HIV incidence) detected with 80% power varying testing coverage and HIV incidence under the standard-of-care (control).

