the Central Limit Theorem,¹ and will use the Student's *t*-distribution with (*J* – 2) as a finite sample approximation to the standard normal distribution.¹⁵

Secondary analyses: To assess the robustness of these findings, we will repeat these analyses using the unadjusted effect estimator. We will also repeat these analyses using TMLE to adjust for missing endpoints.

Subgroup analyses: We will repeat these analyses within strata defined by country, sex, age group, alcohol use, and use of PrEP/PEP in the 6 months before enrollment. To further understand effect heterogeneity, we may conduct variable importance measures (i.e., unadjusted and adjusted predictor analyses) with TMLE.

Secondary endpoints compared by arm: We will implement analogous analyses to evaluate the intervention effect on biomedical covered time at-risk, possession covered time (overall and at-risk), and use-to-possession ratio (overall and at-risk).

Validation of self-report: Since the primary and key secondary study endpoints rely on self-report, we will objectively measure adherence using drug levels in small hair samples collected among participants reporting any PrEP or PEP doses taken in the past 30 days. Overall and by arm, we will report the number and proportion of these participants with detectable tenofovir levels (>0.002 ng/mg) in their hair at week-24. Using a two-sample test, we will formally test the null hypothesis of equal proportions between arms. We may repeat these analyses at week-48.

Additional descriptive analyses: Overall and by arm, we will report the number and proportion of participants who withdrew, died, or seroconverted. We will provide seroconversion narratives and may test the null hypothesis of the HIV incidence rate is the same between arms through Poisson regression with person-years-at-risk as offset.

5. Intervention Implementation

Within the intervention arm, we will describe coverage and uptake of the DCP intervention over follow-up:

- Visit coverage: number and proportion who attended study visits
- Choice of HIV prevention product: number and proportion who selected PrEP, PEP, condoms, or nothing
- Choice of HIV testing: number and proportion who selected a self-test or rapid HIV test
- Choice of service location: number and proportion who selected to have visits at clinic or at an out-of-clinic location (e.g., home)

[figure not shown]

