2.1 General approach for evaluating intervention effects

We will assess the intervention effect with targeted minimum loss-based estimation (TMLE), which provides precision and power gains over an unadjusted effect estimator (e.g., a t-test) by adjusting for baseline predictors of the outcome.⁴⁻⁷ For a detailed review of TMLE and its relation to other effect estimators in randomized trials, we refer the reader to Colantuoni and Rosenblum.⁸ For a recent demonstration of the improved precision offered by TMLE in randomized trials, we refer the reader to Balzer et al. and to Benkser et al.^{9,10}

Here, we will use **TMLE with Adaptive Pre-specification**, a fully automated procedure to flexibly adjust for baseline outcome predictors, while maintaining Type-I error control.^{11,12} Specifically, using 10-fold cross-validation, we will chose the optimal approach for estimating the expected outcome given the trial arm and baseline covariates (a.k.a., the outcome regression) and for estimating the conditional probability of being randomized to the intervention given the baseline covariates (a.k.a., the propensity score). Throughout, optimality is defined by using the squared (estimated) influence curve for the TMLE as loss function. Thereby, we will select the combination of estimators (adjustment variables + approach) for the outcome regression and the propensity score that minimizes the cross-validated risk estimate and, thus, maximizes empirical efficiency.

Our pre-specified, candidate adjustment variables are age, sex, baseline HTN severity as assessed at enrollment (“grade 1” as 140-159/90-99 mmHg; “grade 2” as 160-179/100-109 mmHg, and “grade 3” as $\geq 180/110$ mmHg), country, and nothing (i.e., unadjusted). Our pre-specified candidate estimators are main terms, stepwise

regression, adjustment for a single covariate, and the mean. In sensitivity analyses, we will also implement that unadjusted effect estimator as the contrasts of average outcomes by arm.

Primary estimates will be for the study sample and on the **difference scale**:

$\frac{1}{n} \sum_{i=1}^n [Y_i(1) - Y_i(0)]$, where $Y_i(1)$ denotes the counterfactual outcome for participant i under the intervention and $Y_i(0)$ denotes the counterfactual outcome for participant i under the control. Secondary comparisons will be on the relative scale.

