For all endpoints, we will test the **null hypothesis** of no change in outcomes due to the intervention with a two-sided test at the 5% significance level. We will also report point estimates and 95% confidence intervals for each effect measure and the arm-specific average outcomes. Standard error estimation will be with the estimated influence curve, and statistical inference will follow from the Central Limit Theorem (i.e., using the standard normal distribution).⁴

For all endpoints, we will also examine the intervention effect within subgroups defined by sex, age group (<60 years vs. ≥ 60 years), country, baseline HTN severity, and HIV status. In subgroups with fewer than 51 participants, we will conduct unadjusted analyses.

2.2 Evaluate the effect on hypertension control at week 24 and 48

The primary endpoint is hypertension control at week 24, evaluated in all participants in a research visit at week 24 and defined as blood pressure $< 140/90$ mmHg on the average of the second and third measurements. Participants who miss their week 24 visit and, thus, are missing blood pressure measurement at week 24 will be assumed to be uncontrolled.

As described above, we will use TMLE with Adaptive Pre-specification to compare hypertension control between intervention and control arms and to test the null hypothesis that the intervention did not impact hypertension control. We will conduct sensitivity analyses using TMLE to adjust for differences in characteristics (e.g., arm, age sex, sex, country, baseline severity) between persons with measurements and persons with missing measurements. We may conduct an additional sensitivity analysis excluding participants with missing values.

A secondary endpoint is hypertension control at week 48, assessed in the same manner as hypertension control at week 24.

At week 24 and week 48, we will also evaluate the intervention impact on hypertension severity, defined as participants with grade 2 or higher hypertension. For the severity endpoint, our primary approach will be TMLE to adjust for differences between persons with and without measured outcomes, and the secondary analysis will exclude participants with missing outcomes.

2.3 Evaluate the effect on retention in care at week 24 and 48

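### Severe hypertension SAP: subgroups with fewer than 51 participants drop covariate adjustment but keep a large-sample normal test, which is too liberal at small subgroup sizes

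*SAP*

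**What the plan says.** The severe hypertension SAP (version 1.0, June 2023), section 2.1, sets one inference rule for every endpoint. The null hypothesis is "no change in outcomes due to the intervention with a two-sided test at the 5% significance level". On the standard error it says "Standard error estimation will be with the estimated influence curve", and on the reference distribution that "statistical inference will follow from the Central Limit Theorem (i.e., using the standard normal distribution").

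The next paragraph extends the analysis to subgroups by sex, age group, country, "baseline HTN severity, and HIV status". Its only small-sample provision is "In subgroups with fewer than 51 participants, we will conduct unadjusted analyses". It gives no separate standard error, reference distribution, exact test or minimum size.

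The same section makes the difference scale primary and describes the "unadjusted effect estimator as the contrasts of average outcomes by arm". By contrast, section 4 of the village health team SAP uses a Student's t-distribution with J-2 degrees of freedom "as a finite sample approximation to the standard normal distribution".

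**The concern.** The under-51 rule recognises that adaptive covariate adjustment is unreliable in few participants. The standard normal reference is also a large-sample device, and it is left unchanged. For an unadjusted difference in proportions, the influence-curve standard error with a 1.96 cut-off is the Wald test. An arm in which everyone, or no one, is controlled contributes zero variance. For mean systolic pressure the rule is a z-test with an estimated variance.

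Both produce 95% intervals that are too narrow. The effect is largest in the smallest strata, where chance differences are also largest. The risk is that a chance subgroup difference, for example by HIV status, is reported as a finding.

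**Working it through.** **1. The SAP's own figure.** The power appendix gives 80% power with about 100 per arm for 40% versus 60% controlled, two-sided 5%. Check: (√100 × 0.20 − 1.96 × √(2 × 0.5 × 0.5)) / √(0.4 × 0.6 + 0.6 × 0.4) = (2 − 1.386)/0.693 = 0.886, and Φ(0.886) = 81.2%. The figure reproduces.

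**2. Inputs.**
- Two-sided 5%, influence-curve standard error, normal reference, difference scale: section 2.1.
- Arms of 98 and 102: section 1. Randomization was stratified by country and sex, not by HIV status, so the arm split within an HIV stratum is left to chance.
- Subgroup size: an assumption, because no counts are given. Protocol 15.5.1 plans Phase B with "10% HIV prevalence, and 90% testing coverage". If 10% applied here, 200 participants would include about 20 with HIV. Protocol Table 1 lists 4-19% prevalence for the earlier Kenya/Uganda trial, which would mean 8 to 38 people.

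**3. The test that the rule implies.** With arm sizes n1 and n0, N = n1 + n0, and observed proportions p1 and p0, the mean squared influence curve divided by N is (1/N²)[(N/n1)² n1 p1(1−p1) + (N/n0)² n0 p0(1−p0)] = p1(1−p1)/n1 + p0(1−p0)/n0. This is the unpooled Wald variance. If software uses divisor N−1, it is multiplied by N/(N−1), which is 20/19 for 20 people.

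**4. Type I error, binary endpoint.** All pairs of binomial outcomes were enumerated under equal true rates, and the probability of |p1 − p0|/SE > 1.96 was summed. The results were averaged over the arm splits that arise when N people are drawn from 98 and 102. The ranges cover true rates of 30-70%.

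| Participants | Plan, divisor N | Plan, divisor N−1 | Agresti-Caffo |
|---|---|---|---|
| 20 | 9.0-9.8% | 8.0-8.5% | 4.0-5.0% |
| 30 | 7.1-7.2% | 6.2-6.8% | 4.4-4.7% |
| 40 | 6.6-6.9% | 6.1-6.3% | 4.7-5.0% |
| 50 | 6.3-6.5% | 6.0-6.2% | 4.6-5.4% |

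Newcombe intervals give 4.6-5.8% over the same grid. In the full trial (98 versus 102) the plan's rule gives 5.2-5.6%.

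**5. Mean systolic pressure, normal data, 10 per arm.** Divisor n: 2 × P(t18 > 1.96 × √(9/10)) = 7.9%. Divisor n−1: 2 × P(t18 > 1.96) = 6.6%. An ordinary t-test gives 5.0%.

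**6. Illustration.** Suppose 10/10 versus 7/10 are controlled. The difference is 0.30. The variance is 0 + 0.7 × 0.3/10 = 0.021, so SE = 0.145, z = 2.07, p = 0.038, and the interval is 1.6 to 58.4 points. Agresti-Caffo adds one success and one failure per arm: 11/12 − 8/12 = 0.25, SE = √(0.0764/12 + 0.2222/12) = 0.158, and the interval is −5.9 to 55.9 points.

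**7. Relative scale.** A log relative-risk Wald test with 20 participants rejects 1.0-3.3% of the time for rates of 30-60%, so it is conservative.

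**The case against.** **The subgroup size is not known.** This stands. The 10% prevalence is a Phase B planning input for adults aged 15 and over, in communities that must differ from those in Phase A. This trial enrolled people aged 40 or over with severe hypertension. The result therefore has to be given as a range over sizes.

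**Results at exact arm sizes are jagged.** This also stands. At a 40% rate and divisor N, 10 per arm gives 9.2%, but 12 per arm gives 6.8% and 15 per arm 6.4%. Averaging over chance splits removes most of that, and the excess remains.

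**The SAP does not name the variance divisor.** This is correct. With divisor N−1, an exact 10/10 split gives 6.0% at a 40% rate. Averaged over splits of 20 people, the figure is still about 8%.

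**Unadjusted could mean a t-test.** Section 2.1 mentions one in an aside, as an example of an unadjusted effect estimator. An ordinary t-test at 10 per arm would give about 4%. The aside describes an estimator, however, and the explicit inference rule for all endpoints is the normal reference. If a t-test is intended, the SAP should say so.

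**The illustration can be made to look worse.** A reader might compare p = 0.038 with Fisher's exact p = 0.21. That comparison exaggerates the gap, because Fisher's test at 10 per arm has a true error of only about 1%. A pooled z-test gives p = 0.060, which is a fairer yardstick.

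**The village trial is not a close precedent.** Its t reference serves a main analysis of 16 clusters. It shows that the team knows the device, and no more.

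**Conclusion.** The concern holds as a minor one about subgroup inference. As written, the rule is too liberal below 51 participants on the difference scale: about 9-10% at 20 participants (about 8% with divisor N−1), about 7% at 30-40, and 6.3-6.5% at 50. For mean systolic pressure at 10 per arm it is 6.6-7.9%.

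These figures assume true control rates of 30-70%, independent participants and chance arm splits. They ignore the stratification by country and sex, which could lower the error somewhat.

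Three stronger readings are not supported:
- That every subgroup under 51 has about 9% error. Near the cut-off it is little above 6%.
- That the HIV subgroup is known to have 20 people. No count is given.
- That the trial's main result is affected. The primary test in 98 and 102 participants has close to nominal error, and the secondary relative scale is not inflated at 20 participants. The SAP also attaches no confirmatory claim to its subgroups.

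**What to change.** Add a sentence to section 2.1 of the severe hypertension SAP: in subgroups with fewer than 51 participants, differences in proportions will use Agresti-Caffo (or Newcombe) intervals and the matching test, and mean systolic pressure will use a t reference with n−2 degrees of freedom and variance divisor n−1. Choose one of the two interval methods in advance.

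For proportions, this brings the error to about 4-5% over these sizes with Agresti-Caffo, averaged over splits. Discreteness remains at particular arm sizes: at exactly 25 per arm and a 50% rate, Agresti-Caffo still gives 6.5%, the same as the current rule. For mean systolic pressure with normal data, the t reference gives 5.0%.

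The cost is one sentence and slightly wider intervals in small subgroups. The primary analysis and the larger subgroups do not change.

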2.5 Evaluate the effect on time to hypertension control

Using routine clinical data, we may evaluate the intervention effect on the time to hypertension control (<140/90 mmHg). To conduct such an analysis, we would use Kaplan-Meier to compare the cumulative incidence of attaining hypertension control over the first 24 weeks using routine clinical data and censoring at death.

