Hypertension Treatment intervention	
 1) All participants screened with blood pressure $\geq 160/100$ mmHg will be referred to the nearest clinic for an initial clinical evaluation. In Phase B, participants will be offered the option of ongoing follow-up at home facilitated by a VHT/CHV or in the clinic 2) Participants who do not link to care at a clinic may still be followed at home with VHT/CHV supported telehealth and encouraged to present to clinic for at least one in-person evaluation by a clinician. 3) VHT/CHV home visit frequency determined based on severity of hypertension 4) Hypertension care conducted at home with VHT/CHV measuring blood pressure and phone-based clinician consultation; referral for clinic visits if clinician concerned about symptoms or based on preference 5) Clinician conducts telemedicine visit with patient to ask/answer questions, review blood pressure, prescribe medications 6) VHT/CHV delivers medication from the clinic to the patient 7) VHT/CHV-entered blood pressure and medication data populates dashboard to facilitate population management and CHV supervision by clinician 8) Patients maintain the option of clinic visits for hypertension care if desired

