Treatment: Following community mobilization, study staff will offer community-based screening for hypertension to persons ≥ 40 years old during mobile outreach to community venues. Persons screened who have blood pressure measurements $\geq 160/100$ mmHg after three repeated measurements at a single community-based screening will be eligible for enrollment into the hypertension treatment trial. All persons will have immediate evaluation at clinical center for the hypertension. For follow-up, eligible adults who consent to participate will be randomized to receive follow-up hypertension care at home (intervention) or at the clinic (control) in Phase A. In Phase B, participants will be offered the choice of care at home via VHT/CHV and telehealth, or at the clinic.. All participants will have the option of accessing hypertension care at the clinic if desired, regardless of randomization arm. Hypertension visit frequency (home or clinic-based) will be determined based on severity of hypertension and clinician judgement, with recommended frequency of every 4 weeks if blood pressure is uncontrolled ($\geq 140/90$ mmHg) and every 12 weeks if blood pressure is controlled ($< 140/90$ mmHg). Table 14 describes the schedule of study evaluations.

As per the standard of care, participants with co-morbid diabetes and/or HIV will have the option to receive VHT/CHV medication delivery for these conditions together with their hypertension medications. Medications will be prescribed by the clinician using standard treatment guidelines after completion of phone consultation for standard clinical evaluation. For participants with diabetes, the clinician will order a point-of-care random blood glucose when indicated to guide treatment decisions (to be performed by trained VHT/CHV or self-administered by participant). The clinician will advise the participant to come to the clinic for additional evaluation at any point they feel is clinically indicated.

Table 10. Hypertension Treatment Schedule of Evaluations*

Procedure or Evaluation	Week								
	0 (Baseline)	2	4	8	12	16	24	36	48
Clinical screening for signs/symptoms of secondary hypertension	X								
Creatinine and urinalysis testing*	X								
Clinic visit (intervention)	X								
Clinic visit (control) ^a	X	(X)	X	X	X	X	X	X	X
Home/Community visit (Intervention) ^a		(X)	X	X	X	X	X	X	X
Assessment of adherence, barriers to care, preferences for care site	X						X		X

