*In Phase B, creatinine and urinalysis will be done through standard of care

^aBoth Intervention and Control arms (Phase A) or home and clinic visits (Phase B) will be scheduled every 4 weeks when blood pressure is uncontrolled and every 12 weeks when blood pressure is controlled (shorter intervals of 2 week follow-up should be considered for hypertensive urgency/emergency or at provider discretion in the setting of other clinical concerns). All participants (regardless of care engagement) should have visits by study staff for study measures at week 24 (+/-4 weeks) and week 48 (+/-4 weeks).

9.2.2.5. Social Network Referral Cards for HIV testing.

To better understand strategies to reach persons at risk for HIV and with undiagnosed HIV, and to leverage social networks among persons enrolling in our Phase A studies, we may offer referral cards for HIV testing and multi-disease standard screening (e.g. hypertension) to participants in the study to distribute to their friends or family. This will be done during screening and at out-of-facility outreach testing offerings.

[figure not shown]

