9.4.2. Dynamic Treatment

- The primary outcome for the Mobile Travel Pack and Alcohol Counseling interventions will be viral suppression (HIV RNA<400 cps/ml) at 48 weeks for the mobility trial and 24 weeks for the alcohol trial. Secondary outcomes for the Mobility (“travel pack”) intervention trial may include time retained in care (non-retention defined as the period of time following >2 weeks from a missed clinic visit until return to clinical care) and ART-covered time over 48 weeks. Secondary outcomes for the Alcohol Counseling intervention trial may include viral suppression at 48 weeks, heavy alcohol use at 24 and 48 weeks (measured by self-report and corroborated by phosphatidylethanol [PEth], a valid biomarker of prior 2-3 weeks’ alcohol consumption^{102,102}), and time retained in care (non-retention defined as the period of

time following >2 weeks from a missed clinic visit until return to clinical care) over 24 weeks. The primary outcome for the Hypertensive Linkage Intervention will be linkage to hypertension care at the local government clinic within 30 days of screening positive for high blood pressure during community screening. Secondary outcomes for the Hypertension Linkage intervention trial will include linking to hypertension care on the date of their scheduled appointment and blood pressure control (defined as systolic blood pressure <140 mmHg and diastolic blood pressure <90 mmHg) at 3, 6 and 12 -months post-enrollment. The primary outcome for the hypertension treatment trial will be HTN control at 24 weeks (blood pressure <140/90 mmHg). Secondary outcomes will include time to attaining hypertension control, HTN control at 12 months, proportion retained in care at 24 and 48 weeks.

Process and implementation measures for the Dynamic Treatment measures will be obtained from clinic-based records and logs. Examples that may be evaluated are shown in Table 15. Additional information on mediators will be determined as described in Table 14, with the addition of a sexual behavior and mobility survey.

Table 15. Phase A Dynamic Treatment Process Measures

Setting	Intervention Fidelity	Patient-level Intervention Adoption & Process Outcomes

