After community-based screening by community health workers, individuals with severe hypertension were referred to the nearest government-run clinic for clinical assessment and enrollment. Following enrollment and completion of an initial clinic visit, participants were randomized to the intervention (n=98) or control (n=102) conditions. To ensure balance between arms, randomization was stratified by country and sex and was implemented by an independent statistician using a stratified random block design with random block sizes 2 and 4.

Intervention participants received home-based, follow-up care for hypertension, which consisted of blood pressure measurement and adherence assessment using pill count by a community health worker, a telehealth visit with a clinician, and medication dispensation by the community health worker according to clinician orders. Control participants received clinic-based integrated, patient-centered hypertension care, detailed elsewhere.¹⁻³ Treatment guidelines for use of antihypertensive medication for both study arms were based on standard country guidelines. Additional details of the study procedures are available in the Study Protocol.

The primary objective of this study is to determine whether the intervention improved hypertension control at 24 weeks. Secondary endpoints include retention in care, mean systolic blood pressure at 24 and 48 weeks, and hypertension control at 48 weeks. We will also characterize changes in hypertension severity and evaluate predictors HTN control and retention.

Throughout, the population of interest comprises non-pregnant adults, aged 40+ if blood pressure was elevated at both community-based and clinic measurement (≥ 140 mmHg systolic or ≥ 90 mmHg diastolic) and moderate-severely elevated on at least one of these measurements (≥ 160 mmHg systolic or ≥ 100 mmHg diastolic). Participants were excluded if they were pregnant – these individuals were immediately referred to the prenatal clinic for evaluation and treatment of hypertension in pregnancy.

We will provide descriptions of participant flow through the study (i.e., a consort diagram), measurement coverage, and baseline characteristics (e.g., country, age, sex, prior history of hypertension diagnosis and baseline treatment, comorbidities, and baseline severity of hypertension). We will also report risk factors (N and %) for uncontrolled hypertension at enrollment. We will provide these descriptive statistics, overall and by arm.

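### The optional time-to-control comparison in the severe hypertension trial uses routine readings whose setting and measurer differ by arm, so it could show a spurious difference in either direction

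*SAP*

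**What the plan says.** Section 2.5 of the severe hypertension SAP (version 1.0, 1 June 2023) opens conditionally: "Using routine clinical data, we may evaluate the intervention effect on the time to hypertension control (<140/90 mmHg". If done, the analysis would "compare the cumulative incidence of attaining hypertension control over the first 24 weeks using routine clinical data and censoring at death". Death is the only censoring reason given. The section does not say how many readings a visit needs, whether one value below the threshold is enough, or how missed visits are handled. Section 2.1 applies a two-sided 5% test to every endpoint and makes no exception for this one.

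Who takes the routine reading depends on arm. SAP section 1 gives the intervention arm home follow-up with "blood pressure measurement and adherence assessment using pill count by a community health worker", while "Control participants received clinic-based integrated, patient-centered hypertension care". Table 9 in protocol 9.2.2 agrees: "Hypertension care conducted at home with VHT/CHV measuring blood pressure and phone-based clinician consultation".

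Two protocol statements limit the contrast. Under Table 10 (protocol 9.2.2.4), visits in both arms "will be scheduled every 4 weeks when blood pressure is uncontrolled and every 12 weeks when blood pressure is controlled". The same section adds: "All participants will have the option of accessing hypertension care at the clinic if desired, regardless of randomization arm".

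The outcome's status is not consistent. Protocol 9.4.2 says: "Secondary outcomes will include time to attaining hypertension control". The secondary endpoints listed in SAP section 1 are retention, mean systolic pressure and week-48 control; time to control is not among them.

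**The concern.** The other blood pressure endpoints use a common measurement. Control at weeks 24 and 48 comes from a research visit and averages the second and third readings (SAP 2.2). Mean systolic pressure uses readings taken by research staff (SAP 2.4). Section 2.5 drops that protection. Where and by whom pressure is measured then becomes part of the randomized contrast and cannot be separated from an effect of care.

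The outcome is a first crossing of a threshold, which makes it sensitive in two ways. A systematic difference between home and clinic readings moves people across 140/90 without changing their pressure. And a person who misses visits has no reading, so cannot be recorded as controlled, yet stays in the risk set because only death is censored. The SAP itself compares retention by arm (2.3) and reports completion of a post-baseline visit (2.7), so it treats attendance as something the intervention may change.

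At stake is a result listed as secondary in the protocol. A finding of faster (or slower) control could arise from measurement alone and be read as support for, or evidence against, the primary result.

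**Working it through.** **1. The plan's own figure.** The SAP appendix states 80% power with about 100 per arm for 40% versus 60% control. With pooled variance and a two-sided 5% test:

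n = (1.96·√(2·0.5·0.5) + 0.8416·√(0.4·0.6 + 0.6·0.4))² / 0.20² = (1.3859 + 0.5831)² / 0.04 = 96.9, so 97 per arm.

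At the randomized 98 versus 102, power is 81.2%. The figure reproduces. It belongs to week-24 control at the research visit; no power is stated for time to control.

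**2. One reading, setting only.** Let systolic pressure have SD 18 and mean μ, and let home readings run d mmHg lower (all assumed). The gain in the share below 140 is Φ((140 − μ + d)/18) − Φ((140 − μ)/18).

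- d = 3, μ = 145: Φ(−0.111) − Φ(−0.278) = 0.456 − 0.391 = 6.5 points
- d = 8, μ = 145: Φ(0.167) − Φ(−0.278) = 0.566 − 0.391 = 17.6 points

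**3. First crossing over 24 weeks.** From the documents: 98 versus 102 participants and visits at weeks 4, 8, 12, 16 and 24 in both arms (Table 10, leaving out the bracketed week 2). Assumed: systolic only, baseline mean 165, between-person SD 15, a true fall of 20 mmHg by week 24 in both arms, and visit-to-visit SD 8 or 12. The event is the first attended reading below 140. A missed visit counts as not yet controlled, and no deaths are simulated. The SAP names no specific test, so a two-sided 5% log-rank test was assumed, with 3,000 runs per scenario. True pressure is identical in the two arms throughout. Ranges span the two visit SDs.

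| Home minus clinic (mmHg) | Attendance, intervention / control | Difference in 24-week cumulative incidence (points) | Log-rank rejection |
|---|---|---|---|
| 0 | 90% / 90% | −0.1 to +0.1 | 5.0–5.4% |
| −3 | 90% / 90% | +6.7 to +7.4 | 17–20% |
| −5 | 90% / 90% | +11.1 to +12.2 | 41–46% |
| −8 | 90% / 90% | +17.5 to +19.6 | 80–84% |
| +5 | 90% / 90% | −11.4 to −11.3 | 39–42% |
| 0 | 90% / 80% | +1.9 to +2.3 | 6–7% |
| 0 | 90% / 70% | +4.4 to +5.7 | 11–14% |
| 0 | 95% / 60% | +8.1 to +10.0 | 23–34% |
| −5 | 90% / 70% | +16.6 to +17.0 | 71–74% |

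In every scenario, control on a common research reading at week 24 was equal between arms, at about 38% to 40%. With equal setting and attendance the test keeps its nominal level, so the excess comes from measurement.

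**4. Death.** Kaplan-Meier with death censored estimates the probability of control if death did not occur, not the cumulative incidence. Assume constant hazards, 50% control by 24 weeks on the Kaplan-Meier scale, and mortality q of 1% or 4%. Then λ = −ln 0.5 = 0.693, m = −ln(1 − q), and the cumulative incidence is λ/(λ + m)·(1 − e^−(λ+m)).

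- q = 1%: 0.9857 × 0.505 = 49.8%, 0.2 points below Kaplan-Meier
- q = 4%: 0.9444 × 0.520 = 49.1%, 0.9 points below

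If mortality is similar in the arms, this largely cancels from the contrast.

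**The case against.** The strongest reply is that the analysis is optional, is missing from the SAP's own secondary list, and sits beside two endpoints that measure blood pressure properly. That is correct, and it limits the point to one supporting analysis. It does not settle it, because protocol 9.4.2 still lists the outcome and SAP 2.1 would attach a test to it.

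Several stronger readings are tempting but are not supported:

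- A reader might infer that home care is scheduled for more readings. Table 10 gives both arms the same visits under the same rule, so only attended or unscheduled readings can differ. Comparing a person read once with a person read four times is therefore not a contrast this design implies. Attendance effects of about 2 to 10 points are the relevant ones, and the upper end needs 95% against 60%.
- A reader might infer that the bias favours home care. Neither document gives a home-clinic offset, and a reversed offset reverses the bias.
- A reader might set these sizes against the 20-point effect in the power calculation. That figure concerns the research-visit endpoint, which this issue does not touch.
- A reader might conclude that the arm comparison should be removed. Enrolment began in May 2022 and all 200 participants (98 + 102) are randomized; dropping a protocol-listed outcome now would invite its own criticism. Labelling and sensitivity analysis are enough.

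The right of any participant to use the clinic dilutes the setting contrast by an unknown amount. It does not remove it.

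**Conclusion.** The concern holds in limited form. As written, the section 2.5 comparison could show a difference between arms with no difference in true blood pressure, and the sign is not known in advance. Under an assumed home-clinic offset of 3 to 8 mmHg the artefact is about 7 to 20 points in 24-week cumulative incidence. Attendance differences alone give about 2 to 10 points. These sizes rest on assumed offsets, variances, blood pressure fall and attendance, and they ignore clinic use by intervention participants. What comes from the documents is the link between arm and measurement setting, and the absence of any rule in 2.5 to deal with it. Censoring at death is a real but probably small error. The primary week-24 endpoint, week-48 control and mean systolic pressure are not exposed.

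**What to change.** Amend SAP 2.5 as follows:

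- Label the routine-data analysis exploratory and descriptive, with no hypothesis test, and exempt it from the general test in 2.1.
- State that between-arm conclusions on control rest on the week 24 and week 48 research measurements.
- Report the number and setting of routine readings by arm.
- Treat control as interval-censored between attended visits.
- Add a sensitivity analysis that shifts home readings over a stated range in both directions.
- Treat death as a competing event (Aalen-Johansen) instead of censoring it.
- Reconcile the outcome's status between protocol 9.4.2 and SAP sections 1 and 2.5.

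The cost is SAP wording, a short protocol clarification and a little more analysis. No new data, visits or participants are needed. What is given up is a formal test of time to control.
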